8.	Intradialytic Clonidine Use	This can acutely influence intradialytic blood pressure in an ECV-independent way. This is used to treat severe hypertension during dialysis, and these patients frequently have ECV-independent etiology of hypertension, including possible medication non-adherence	
9.	Documented Antihypertensive Medication Non-adherence	This can acutely influence intradialytic blood pressure in an ECV-independent way.	
Aim 1 C			
10.	Amputated Extremity (excluding fingers, toes, hands, or feet)	Bioimpedance measurements of extracellular water are less accurate if all 4 major limbs are not present.	
11.	Presence of cardiac defibrillator, pacemaker	The current from the bioimpedance electrodes may interfere with the function of these devices	
12.	Presence of metal prostheses	Bioimpedance measurements are less accurate if implanted metal is present	

Eligible subjects agreeing to participate in all aims will be assigned to one of two study groups based on computer-generated randomization stratified by gender: IBPS-based management or Standard of Care (detailed in Aim 2). The presence of contraindications to BIA (see Table 1, #10-12) would not exclude a subject from participating in Aims 2 and 3. Such subjects would complete all study procedures except the BIA and NICOM. The outcomes of Aims 2 and 3 (ambulatory blood pressure and intradialytic hypotension) would still be ascertained. Eligible subjects not willing to undergo randomization into a 16 week trial (Aims 2-3) may participate in the BIA and measurements in Aim 1 only.

In short subjects may participate in Aim 1 only, Aims 2 and 3 only, or all Aims based on individual exclusion criteria and preference. We have successfully recruited more than 125 HD patients over the past several years for various prospective research studies and continue to maintain support from DaVita dialysis units (see Letters of Support).

Study Procedures: All procedures will be conducted by authorized personnel from the UT Southwestern research team consisting of the principal investigator and research nurses/coordinators.

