### Statistical Analysis Plan and Power Calculation for Sample Size (Aim 1)

This aim's primary outcome is the correlation between mean IBPS and post-HD ECV/body weight. We will determine this with Pearson correlation analysis. In our preliminary data analysis of 49 HD patients, we demonstrated a significant association between ECV/body weight and systolic IBPS from one HD treatment (r=0.4, p=0.008). We aim to establish that an even stronger correlation exists in a more homogeneous population with less extremes of blood pressure and blood pressure changes (see Exclusion criteria 3-8 above). We also aim to establish associations within each gender. Assuming 80% power at a 0.05 significance level, we would need the following sample sizes to show the following correlations: 15 subjects for r=0.6, 23 subjects for r=0.5, 33 subjects for r=0.4 using Pearson correlation analysis. To confirm our assumption of normal distribution, we would need at least 30 subjects. We intend to recruit at least 66 subjects (33 of each gender) to ensure that we can demonstrate a strong correlation within each gender. Our expected Aim 2 sample size is 74 subjects (most of which will have BIA measurements), so we expect to have more than adequate sample size for Aim 1. Exploratory analyses will include correlation of ECV/body weight with diastolic blood pressure slope and overall change in blood pressure from pre to post dialysis as well as correlations involving ECV/total body volume with IBPS.

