# **Outcomes** During The Study:

Ambulatory Blood Pressure: The mean ambulatory systolic blood pressure will be the primary dependent variable. We selected this variable because it is the blood pressure metric that best predicts mortality in HD patients[12]. Unlike BIA or NICOM, no subjects that would be excluded from obtaining ambulatory blood pressure measurements in this study. All subjects will have baseline measurements of ambulatory blood pressure at week 0 following a mid-week treatment. It will be repeated at week 16 following a mid-week treatment.

*BIA and NICOM:* At baseline (week 0), all eligible subjects will undergo BIA and NICOM for measurements of ECV/body weight (see Aim 1) and total peripheral resistance index before and after a mid-week treatments. The procedures will all be repeated at week 8 and week 16 following a mid-week treatment.

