### **Statistical Analysis Plan and Power Calculation for Sample Size (Aim 2)**

The primary outcome of this aim will be the ambulatory systolic blood pressure from baseline to 16 weeks. Secondary endpoints include ECV/body weight and total peripheral resistance, from baseline to 16 weeks. We will use the two-sample t test to perform the unconditional comparison of the difference in endpoints over time between treatment and control groups. For conditional comparison, we will use the linear mixed effect model to estimate the fixed effect of the treatment group indicator, while adjusting for the fixed effects from baseline variables and time and the random effect within the same patient. We determined our sample size based on known effects of intense ultrafiltration on ambulatory blood pressure reduction. In the DRIP trial[10], systolic blood pressure decreased by 13.9 mmHg in the intense ultrafiltration group and 6.9 mmHg in the standard group (95% CI -12.2 − 1 mmHg) after 8 weeks. We expect a more modest decrease in systolic blood pressure due to our less aggressive approach per treatment. Assuming a standard deviation for the ambulatory systolic blood pressure change of 6 mmHg (this was approximately 2.7 mmHg in DRIP and our study will have a smaller sample size), we will be able to show with 90% power and an alpha of 0.05, that a between group difference ≥2.7 mmHg will occur. If the normality assumption indeed holds in our observed data, this would require 14 subjects per arm, but we will recruit 30 subjects per arm to facilitate simple normality check such as the Q-Q plot. Assuming a 25% dropout rate, we will aim to recruit 74 subjects (37 in each group).

With our sample size (n=74), we will have 85% power to detect a 0.025 difference in the change between groups after 16 weeks in ECV/body weight. This clinically significant difference is consistent with the difference in post-HD ECV/body weight we found in patients with intradialytic hypertension and HD controls [13]. Based on our prior experiences recruiting HD patients for clinical research, we expect that we will be able to enroll 1-2 patients each month (18 patients each year including excluding dropouts).

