### POTENTIAL PROBLEMS AND ALTERNATIVES (Aim 2)

In the unlikely event our Aim 1 hypothesis is proven invalid and fails to show as robust association between IBPS and ECV as hypothesized, the evidence remains strong that intensifying ultrafiltration lowers blood pressure. Aim 2 will provide an opportunity to determine if an algorithmic alternative to the arbitrary prescription approach in standard care is more effective at achieving that goal, and it will provide a mechanistic assessment of how gradual changes in ECV impact vascular resistance and cardiac output in HD patients.

[figure not shown]
Potential problems in Aim 2 include the possibility that patients with severely uncontrolled BP will need major changes in antihypertensive medications during the study. In this case, blood pressure slopes may be modified despite no change to the patient's ECV. We will minimize this risk by excluding patients with poor control of blood pressure (pre or post HD systolic BP> 180 mmHg) and history of medication non-adherence. In the unlikely event that our intervention fails to improve blood pressure or ECV in the overall population, we will be able to explore which subgroups did appear to achieve benefit so that we can further refine our algorithm.

In some clinical studies, measurements obtained with BIA have been used to guide fluid removal. The inability to include subjects with amputations, cardiac defibrillators or pacemakers in the 16 week clinical trial would reduce our ability to achieve the necessary sample size and would limit our ability to generalize our findings to many other hypertensive HD patients. Subsequently, the measurements obtained with BIA in this aim will only be used as secondary outcomes among those subjects that have no exclusion criteria for its use. Another potential marker for ECV excess that has been considered is the slope of intradialytic hematocrit using relative blood volume monitoring as an estimate of intravascular volume. Our primary concern with this is that the device used for this application is currently on FDA recall. Furthermore, there is prior evidence from a randomized trial showed that mortality and hospitalization increased in patients who had blood volume monitoring[14].

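### Recruiting 37 per group with 25% dropout leaves 27–28 per arm, not 30, and the 85% power for ECV/body weight is stated on all 74 recruits with no allowance for dropout or missing BIA

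*Combined protocol and SAP*

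**What the plan says.** The figures are in the Statistical Analysis Plan and Power Calculation for Sample Size (Aim 2). After deriving 14 per arm for the primary endpoint, the section raises the number: "but we will recruit 30 subjects per arm to facilitate simple normality check such as the Q-Q plot". It then allows for attrition: "Assuming a 25% dropout rate, we will aim to recruit 74 subjects (37 in each group"). The next paragraph turns to the secondary endpoint: "With our sample size (n=74), we will have 85% power to detect a" 0.025 difference between groups in the change in ECV/body weight after 16 weeks. No SD for that change is given, and no evaluable number.

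The same section names the analysis: "We will use the two-sample t test to perform the unconditional comparison of the difference in endpoints over time between treatment and control groups". It adds a linear mixed model that adjusts for baseline variables and time.

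Three other places bear on how many patients will have the ECV measurement:

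- Section 1.A (Patient Population) admits patients with BIA contraindications to Aims 2 and 3: "Such subjects would complete all study procedures except the BIA and NICOM".
- The Aim 1 sample-size section says: "Our expected Aim 2 sample size is 74 subjects (most of which will have BIA measurements").
- Potential Problems and Alternatives (Aim 2) restricts BIA to secondary outcomes "among those subjects that have no exclusion criteria for its use".

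BIA is taken at week 0, and the outcomes section for Aim 2 adds: "The procedures will all be repeated at week 8 and week 16 following a mid-week treatment".

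**The concern.** Two stated figures appear not to follow from the plan's own assumptions.

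First, 37 per group is evidently 30 inflated for dropout, but removing 25% of 37 does not return 30.

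Second, the ECV/body weight power is attached to the recruited number, immediately after the plan has assumed that a quarter of those patients will be lost. A t test on the change from week 0 to week 16 can use only patients with BIA at both visits. It loses the dropouts and also the randomised patients who never have BIA.

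The stake lies mainly in the second figure. Lower ECV is part of the project's central hypothesis, and Expected Outcomes (Aim 2) predicts a difference of at least 0.025. A null result on this endpoint would be read against a stated 85% power. If the real power is nearer 65–75%, that reading would be too confident.

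**Working it through.** **Inputs.** From the Aim 2 sample-size section: 30 per arm, 25% dropout, 37 per group (74), 85% power, difference 0.025, two-sample t test on change. The same section gives alpha 0.05 for the primary endpoint; I assume it applies here too, two-sided. The SD of the ECV/body weight change and the share of patients without BIA are not in the documents.

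**Step 1: reproduce the recruitment figure.**

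- Multiplying by (1 + d): 30 × 1.25 = 37.5 per arm. This is the only simple rule that comes close to 37 per group (74).
- Dividing by (1 − d): 30 / 0.75 = 40 per arm, 80 in total. This does not give 74.

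The inflation was therefore probably done as N × (1 + d), whereas keeping N completers requires N / (1 − d).

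**Step 2: what 37 per group yields.**

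- 37 × 0.75 = 27.75 per arm, and 74 × 0.75 = 55.5 in total.
- 37 recruits leave 30 only if dropout is at most 1 − 30/37 = 18.9%.

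**Step 3: ECV/body weight power.** The 85% cannot be reproduced without an SD. I solved for the SD that makes it true at a given n per arm, then recomputed power at smaller n. Power is from the noncentral t distribution with 2n − 2 degrees of freedom and noncentrality (0.025/SD) × √(n/2).

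- (a) 85% taken literally at 37 per arm. The required standardised difference is 0.706, so SD = 0.025/0.706 = 0.0354.
- (b) 85% computed on 30 per arm. The required standardised difference is 0.787, so SD = 0.025/0.787 = 0.0318.

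| Patients per arm with paired BIA | Power (a) | 85%-detectable difference (a) | Power (b) | 85%-detectable difference (b) |
|---|---|---|---|---|
| 37 (all recruits) | 85% | 0.025 | 92% | 0.022 |
| 30 | 77% | 0.028 | 85% | 0.025 |
| 27.75 (after 25% dropout) | 73% | 0.029 | 82% | 0.026 |
| 24.98 (10% of completers without BIA) | 69% | 0.031 | 78% | 0.028 |
| 22.2 (20% of completers without BIA) | 63% | 0.033 | 73% | 0.029 |

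The 10% and 20% shares are assumptions, shown to give a range.

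**Step 4: when would 85% survive?** At 27.75 per arm the required standardised difference is 0.819, so the SD must be at most 0.025/0.819 = 0.0305, and every completer must have BIA. The documents say that not every randomised patient will.

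**The case against.** The best case for the plan has four parts.

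- **The 30 is not a power requirement.** It supports a Q-Q plot, which is about as informative with 27–28 per arm. The plan also uses the word recruit for both 30 and 37, so reading 30 as completers is an inference. This stands: the first part is an arithmetic slip with little consequence.
- **Without an SD the 85% cannot be refuted.** It may have been computed on 30, or even on about 28 completers. This stands as a limit on the size of the loss, which is why two scenarios are shown. It does not rescue the statement, which names n=74 and gives the reader no means of checking it. Even a calculation on 28 completers would leave out patients without BIA.
- **The mixed model may do better than the t test.** It can use week-8 BIA from patients who drop out later, and baseline adjustment can reduce the residual SD. For example, if baseline ECV/body weight is a covariate, variances are equal and the baseline-to-week-16 correlation is 0.5 (an assumption), the SD shrinks by √((1 + 0.5)/2) = 0.87. Scenario (a) then gives about 85% at 27.75 per arm; with correlation 0.7 it gives about 80%. This is a fair point about the power the trial may achieve. However, the plan does not tie the 85% to that model, and the model cannot recover patients who never have BIA. Whichever analysis had 85% power on 74 patients has less on about 55.
- **The plan acknowledges missing BIA.** It does so in words, but the power statement contains no numerical allowance.

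It can also be said that the primary-endpoint calculation in the same section is the larger problem: 2.7 mmHg with SD 6 mmHg, two-sided 0.05 and 90% power needs 104 per arm, not 14. That is a separate matter and does not make these two figures right.

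**Conclusion.** The concern holds. With the plan's own dropout rate, 74 recruits yield about 55 completers, not 60. This follows from the stated figures alone and is minor in effect.

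The material part is the ECV/body weight power. The 85% is stated on a number of patients that the plan itself says will not be available for this endpoint. For the planned t test, the loss from dropout alone is 12 percentage points (85% to 73%) if the statement is taken literally, and 3 points (85% to 82%) if the calculation was in fact made on 30 per arm. Missing BIA lowers both further. These sizes rest on two-sided alpha 0.05, an SD inferred from the stated power, and assumed shares without BIA. That the statement allows for neither loss does not rest on any of these. As this is a secondary endpoint, the point should be corrected but does not threaten the trial's primary conclusion.

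**What to change.** In the Aim 2 sample-size section:

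1. State that 74 recruits with 25% dropout are expected to give about 55 evaluable patients, 27–28 per arm, in place of 30 per arm.
2. For ECV/body weight, state the SD of the 16-week change that was used and its source, the sidedness and alpha, and whether the power refers to the t test or the mixed model.
3. State the expected number with BIA at both week 0 and week 16, after dropout and after removing patients with contraindications.
4. Replace the 85% with the power for 0.025, or the difference detectable with 85% power, on that number. If the 85% was computed on 74 for the t test, the new figure will be about 73% or less.

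The cost is wording and a less favourable power figure for a secondary endpoint. No extra enrolment is needed for this correction. If the sample size is later re-derived for the primary endpoint, these figures should be redone with it, using division by (1 − dropout).

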# **EXPECTED OUTCOMES (Aim 2)**

We expect the IBPS-based ultrafiltration group to have ≥3 mmHg greater reduction in mean ambulatory systolic blood pressure from baseline to 16 weeks than the standard care group. We expect that such differences could be as high as 7 mmHg based on the DRIP trial. Because our algorithm assigns fluid removal objectively and most hypertensive HD patients have ECV excess that is difficult to identify clinically, we expect that subjects assigned to our algorithm will be assigned more fluid removal over the course of the study than those in the standard care group. We expect the outcomes to include improvement in chronic ECV excess as shown by greater reduction in post-HD ECV and ECV/body weight. We expect to also see reduction in post-HD total peripheral resistance. We do expect ambulatory blood pressure to decrease in the standard care group due to patient motivated lifestyle changes while in a clinical trial. However, we expect that the decrease in blood pressure will be of greater magnitude in our IBPS-based ultrafiltration group as specified above. We expect our algorithm will optimize fluid removal and that the change in post-HD ECV/body weight will be ≥0.025 in the IBPS-based ultrafiltration group compared to standard care.

### POTENTIAL PROBLEMS AND ALTERNATIVES (Aim 2)

In the unlikely event our Aim 1 hypothesis is proven invalid and fails to show as robust association between IBPS and ECV as hypothesized, the evidence remains strong that intensifying ultrafiltration lowers blood pressure. Aim 2 will provide an opportunity to determine if an algorithmic alternative to the arbitrary prescription approach in standard care is more effective at achieving that goal, and it will provide a mechanistic assessment of how gradual changes in ECV impact vascular resistance and cardiac output in HD patients.

[figure not shown]
Potential problems in Aim 2 include the possibility that patients with severely uncontrolled BP will need major changes in antihypertensive medications during the study. In this case, blood pressure slopes may be modified despite no change to the patient's ECV. We will minimize this risk by excluding patients with poor control of blood pressure (pre or post HD systolic BP> 180 mmHg) and history of medication non-adherence. In the unlikely event that our intervention fails to improve blood pressure or ECV in the overall population, we will be able to explore which subgroups did appear to achieve benefit so that we can further refine our algorithm.

In some clinical studies, measurements obtained with BIA have been used to guide fluid removal. The inability to include subjects with amputations, cardiac defibrillators or pacemakers in the 16 week clinical trial would reduce our ability to achieve the necessary sample size and would limit our ability to generalize our findings to many other hypertensive HD patients. Subsequently, the measurements obtained with BIA in this aim will only be used as secondary outcomes among those subjects that have no exclusion criteria for its use. Another potential marker for ECV excess that has been considered is the slope of intradialytic hematocrit using relative blood volume monitoring as an estimate of intravascular volume. Our primary concern with this is that the device used for this application is currently on FDA recall. Furthermore, there is prior evidence from a randomized trial showed that mortality and hospitalization increased in patients who had blood volume monitoring[14].

4. AIM 3: The premise for this aim is there is a need for fluid management approaches that minimize intradialytic hypotension. The objective of this aim is to demonstrate how IBPS-based ultrafiltration prescriptions affect intradialytic hypotension. We will test the working hypothesis that in a randomized trial (Aim 2) using IBPS to guide ultrafiltration, the frequency of intradialytic hypotension, the intradialytic systolic blood pressure nadir, and the occurrence of intradialytic symptoms will be similar in subjects randomized to our algorithm and standard care.

Recurrent intradialytic hypotension, defined as systolic blood pressure <90 mmHg) is a mortality risk factor, such that blindly and aggressively removing large amounts of fluid to manage ECV excess may cause

more harm than good in some patients with ECV excess. For HD patients that cannot adhere to the strict dietary sodium and fluid restriction recommendations, there is currently no standardized approach to remove sufficient fluid during dialysis to prevent ECV excess without inducing large decreases in blood pressure. In our preliminary data, the nadir systolic blood pressure is significantly lower in patients in lower quartiles of IBPS (more negative slopes) compared to the upper quartiles (positive slope) as shown in **Figure 4.** Our graded ultrafiltration algorithm assigns less ultrafiltration to those patients with steep negative slopes and therefore avoids overly aggressive fluid removal in patients that are least likely to tolerate it.

### **EXPECTED OUTCOMES (Aim 3)**

We expect that the risk of intradialytic hypotension will be similar in subjects randomized to IBPS-based ultrafiltration and standard care. Because of our exclusion criteria, we do not expect intradialytic hypotension to be common in our clinical trial subjects. We expect our graded algorithm to appropriately balance the intensity of ultrafiltration with the baseline intradialytic hypotension risk. This balanced approach will be reintroduced every month in the intervention group with reassessment of the IBPS. Therefore, we do not expect the incidence of intradialytic hypotension to increase much more than baseline in this same group. We also expect the nadir systolic blood pressure and number of treatments with cramps and dizziness to be similar in the two groups. If these outcomes are similar, we will interpret this as an indication that our algorithm does not introduce any new risk to patients compared to standard care and is a safe alternative that requires evaluation in a long term clinical trial.

### POTENTIAL PROBLEMS AND ALTERNATIVES (Aim 3)

In the event that Aim 2's hypothesis is proven invalid, it is still necessary to known if our algorithmic approach to standard care ultrafiltration causes less intradialytic hypotension.

Because intradialytic hypotension and ultrafiltration rate are strongly associated, another approach to minimize the risk for intradialytic hypotension is to slow the ultrafiltration rate. While lowering the target ultrafiltration volume would achieve this, it would simultaneously increase the risk for ECV excess. Lengthening the dialysis treatment time is another strategy that enables similar (or more) absolute fluid removal at a slower rate. The major limitation of this approach is the logistic application to the population of nearly 500,000 ESRD patients on HD in the United States. Survey data has demonstrated a general unwillingness of HD patients to come in for extra treatments or have increased dialysis time on a regular basis[16]. It is critical to develop a novel approach that remains applicable to the present environment of dialysis care. Furthermore, our approach would remain relevant even in the context of an institutionalized increase in dialysis times.

